7.5 Reporting to the Food and Drug Administration (FDA)

Not applicable.

7.6 Reporting to the NIH Office of Biotechnology Activities (OBA)

Not applicable.

7.7 Reporting to the Institutional Biosafety Committee (IBC)

Participating investigators will register and report on research protocols involving biohazards (i.e., recombinant DNA or infectious agents) according to the reporting requirements set by their respective IBC.

The study will be conducted in accordance with ethical principles founded in the Declaration of Helsinki. The IRB/IEC and other appropriate institutional regulatory bodies will review all appropriate study documentation in order to safeguard the rights, safety, and well-being of the subjects. The study will only be conducted at sites where IRB/IEC and other appropriate institutional regulatory body approvals have been obtained. The protocols, informed consents, written information given to the subjects, safety updates, annual progress reports, and any revisions to these documents will be provided to the IRB/IEC and other appropriate institutional regulatory bodies by the Investigator.

7.8 Reporting to Hospital Risk Management

Participating investigators will report to their local Risk Management office any participant safety reports, sentinel events or unanticipated problems that require reporting per institutional policy.

7.9 Routine Adverse Event Reporting

All Adverse Events **must** be reported in routine study data submissions to the Overall PI on the toxicity case report forms. **AEs reported through expedited processes (e.g., reported to the IRB, FDA, etc.) must also be reported in routine study data submissions.**

Adverse event (AE) monitoring and reporting is a routine part of every clinical trial. The following list of reported and/or potential AEs (Section 8.1) and the characteristics of an observed AE (Section 8.2) will determine whether the event requires expedited reporting **in addition** to routine reporting.

8. BIOMARKER, CORRELATIVE, AND SPECIAL STUDIES

8.1 Biomarker Studies

N/A, no biomarker studies.

8.2 Laboratory Correlative Studies

Biomarker analysis will be performed on blood and tumor samples to evaluate predictive and pharmacodynamic markers for CD19-targeted CAR T cell therapy. Prognostic markers specific for large B-cell lymphoma and related to the tumor immune environment may also be evaluated in archived and fresh tumor biopsies.

The presence, expansion, persistence, and immunophenotype of transduced anti-CD19 CAR T cells will be monitored in the blood primarily by PCR analysis, complemented by flow cytometry. Expansion and persistence in peripheral blood will also be monitored by a CD19 CAR specific quantitative polymerase chain reaction assay (qPCR).

Levels of serum cytokines will be evaluated in serum **to characterize the pharmacodynamic and safety profile of CAR T cell therapy before and after radiotherapy**. The following pro-inflammatory, homeostatic and immune modulating cytokines may be included in the panel: IL-6, IL-15, IL-17a, TNF- α , GM-CSF, IFN- γ , IL-12p40/p70 and IL-13; immune effector molecules: Granzyme A, B and Perforin; correlates of acute phase response: CRP and SAA; Chemokines MIP-1 α , MIP-1 β , MCP-1, IP-10, and IL-8. In addition, IL1Ra, IL2R α and ferritin, will also be measured.

Additional translational samples of PBMC, serum cytokines, tissue, and bone marrow may be taken for additional genomics sequencing, RNA expression profiling, cytokine/biomarker analysis and flow cytometry, and tumor profiling. This may also include tumor samples for genomic, transcriptional and protein expression analysis. Samples will be analyzed within a local immune monitoring facility.

9. STUDY CALENDAR

Assessments must be performed prior to administration of any study agent. Study assessments and agents should be administered within \pm 28 days of the protocol-specified date, unless otherwise noted.

Research staff should refer to the SOAs for an outline of the procedures required. The visit schedule is calculated from **RT start date**. An overview of study assessments/procedures is outlined below.

9.1 Informed Consent

Before a subject's participation in the clinical study, the investigator is responsible for obtaining written informed consent from the subject after adequate explanation of the study design, anticipated benefits and the potential risks. Subjects should sign the most current IRB/IEC approved ICF prior to any study specific activity or procedure is performed.

The consent process and the subject's agreement or refusal to participate in the study is to be

documented in the subject's medical records. If the subject agrees to participate, the ICF is to be signed and personally dated by the subject and by the person who conducted the informed consent discussion. The original signed ICF will be retained in accordance with institution policy and IRB/IEC requirements with a copy of the ICF provided to the subject.

All subjects who are enrolled into the study should be re-consented with any updated version of the IRB/IEC approved ICF if relevant to their participation in the study.

9.2 Demographic Data

Demographic data will be collected to include sex, age, race, ethnicity, and country of enrollment to study their possible association with subject safety and treatment effectiveness.

9.3 Medical and Treatment History

Relevant medical history prior to the start of adverse event reporting will be collected. Relevant medical history is defined as data on the subject's concurrent medical condition that would be typically shared in a referral letter. All findings will be recorded in the CRFs.

In addition to the medical history, all history related to the subject's disease, treatment and response to treatment will be collected and must date back to the original diagnosis.

For subjects who are being referred from another clinic or institution to the participating research center, copies from the subject's chart should be obtained.

9.4 Physical Exam, Vital Signs, Performance Status

Physical exams will be performed during screening and at times noted in the SOA. Changes noted in subsequent exams when compared to the baseline exam will be reported as an adverse event.

Performance status as measured by the ECOG scale will be performed to quantify the subject's general well-being and ability to perform activities of daily life.

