7.2 Adverse Events

An adverse event is defined as any untoward medical occurrence in a clinical trial subject. The event does not necessarily have a relationship to treatments provided leading to study eligibility. The investigator is responsible for ensuring that any adverse events observed by the investigator or reported by the subject are recorded in the subject's medical record.

The definition of adverse events includes worsening of a pre-existing medical condition. Worsening indicates that the pre-existing medical condition has increased in severity, frequency, and/or duration or has an association with a worse outcome. A pre-existing condition that has not worsened during the study or involves an intervention such as elective cosmetic surgery or a medical procedure while on study, is not considered an adverse event.

Interventions for pretreatment conditions (such as elective cosmetic surgery) or medical procedures that were planned before study participation are not considered adverse events. Hospitalization for study treatment infusions or precautionary measures per institutional policy are not considered adverse events.

The term “disease progression” as assessed by measurement of malignant lesions on radiographs or other methods should not be reported as adverse events. Death due to disease progression in the absence of signs and symptoms should be reported as the primary tumor type (e.g., B-Cell Lymphoma).

For situations when an adverse event or serious adverse event is due to the disease under investigation report the signs and symptoms. Worsening of signs and symptoms of the malignancy under study should also be reported as adverse events in the appropriate section of the CRF.

The investigators clinical judgment is used to determine whether a subject is to be removed from treatment due to an adverse event. In the event a subject request to withdraw from protocol required therapies or the study due to an adverse event, the subject should undergo the procedures outlined in the Month 3 visit of the SOA.

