7.4 Procedures for AE and SAE Collection and Reporting

7.4.1 Reporting of Adverse Events

The investigator is responsible for ensuring that all adverse events observed by the investigator or reported by the subject that occur from enrollment (ie, radiation therapy consultation) through 3 months after RT are monitored and reported. After 3 months, targeted adverse events including (eg, neurological, hematological, infections, autoimmune disorders, and secondary malignancies) will be monitored and reported for 6 months after treatment with axicel or tisacel or until disease progression, whichever occurs first.

The investigator must address the below for adverse events:

- Adverse event diagnosis or syndrome (if not known, signs or symptoms)
- Dates of onset and resolution
- Severity
- Assessment of relatedness to investigational product, lymphodepleting chemotherapy or study procedures
- Action taken

In reviewing adverse events, investigators must assess whether the adverse event is possibly related to 1) CAR T cell therapy product 2) RT, or 3) any protocol-required study procedure. The relationship is indicated by a yes or no response and entered into the CRF. A yes response should indicate that there is evidence to suggest a causal relationship between the study treatment or procedure and the adverse event. Additional relevant data with respect to describing the adverse event will be collected in the CRFs.

The investigator is responsible for reviewing laboratory test results and determining whether an abnormal value in an individual study subject represents a clinically significant change from the subject's baseline values. In general, abnormal laboratory findings without clinical significance (based on the Investigator's judgment) are not to be recorded as adverse events. However, abnormal laboratory findings that result in new or worsening clinical sequelae, require therapy or adjustment in current therapy are considered adverse events. Where applicable, clinical sequelae (not the laboratory abnormality) are to be recorded as the adverse event.

The investigator is expected to follow reported adverse events until stabilization or resolution. If a subject begins a new anticancer therapy, the adverse event reporting period for non-serious adverse events ends at the time the new treatment is started.

7.4.2 Reporting of Serious Adverse Events and Non-serious CRS events Grade ≥ 3

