12.1 Study Endpoints

Primary Endpoint:

- Rate and severity of RT-related toxicity as per CTCAE v5.0 criteria during RT or within the first 30 days of completing RT.

Secondary Endpoints:

- **Duration of response (DOR):** Among subjects who experience an objective response, DOR is defined as the date of their first objective response (which is subsequently confirmed) to disease progression per Lugano criteria¹ or death regardless of cause. Subjects not meeting the criteria for progression or death by the analysis data cutoff date will be censored at their last evaluable disease assessment date and their response will be noted as ongoing.
- **Objective response rate (ORR) per IRRC:** ORR per IRRC is defined as the incidence of either a complete response or a partial response by Lugano criteria¹ as determined by the IRRC. All subjects that do not meet the criteria for an objective response by the analysis data cutoff date will be considered non-responders.
- **Progression-free Survival (PFS):** PFS is defined as the time from RT completion date to the date of disease progression per Lugano criteria¹ or death from any cause. Subjects not meeting the criteria for progression by the analysis data cutoff date will be censored at their last evaluable disease assessment date.

- **Overall survival (OS):** OS is defined as the time from RT completion to the date of death. Subjects who have not died by the analysis data cutoff date will be censored at their last contact date.

Exploratory Endpoints:

- Levels of anti-CD19 CAR T cells in blood
- Levels of cytokines in serum
- Incidence of anti-axicabtagene ciloleucel antibodies
- Investigation of potential biomarker development based on assessment of blood cells, tumor cells and the proposed actions of the investigational product.

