12.4 Analysis of Primary and Secondary Endpoints

Planned Method of Analysis

The primary analysis of all treated subjects will take place once they have had the opportunity to be followed for 6 months.

Descriptive analyses may occur at any time.

Objective Response Rate

The incidence of objective response and exact 2-sided 95% confidence intervals will be generated.

Duration of Response

The competing-risk analysis method ^{24,25} will be used to estimate the cumulative incidence of relapse. The cumulative incidence of relapse in the presence of non-disease related mortality (the competing risk) will be estimated along with 2-sided 95% confidence intervals at 3-month intervals.

Progression-free Survival

Kaplan-Meier estimates and 2-sided 95% confidence intervals will be generated for progression-free survival time. Estimates of the proportion of subjects alive and progression-free at 3-month intervals will be provided.

Overall Survival

Kaplan-Meier estimates and 2-sided 95% confidence intervals will be generated for OS. Estimates of the proportion of subjects alive at 3-month intervals will be provided.

Safety

Subject incidence rates of adverse events including all, serious, fatal, CTCAE version 5.0 Grade 3 or higher and treatment related AEs reported throughout the conduct of the study will be tabulated by preferred term and system organ class. Changes in laboratory values and vital signs will be summarized with descriptive statistics. The incidence of concomitant medications will be summarized.

Tables and/or narratives of deaths through the long-term follow-up and treatment related SAEs will be provided.

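### Section 9.4 turns any change from the baseline physical exam into an adverse event, which contradicts the definition in 7.2 for improved and neutral findings

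*Combined protocol and SAP*

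**What the plan says.** Section 9.4 covers the physical exams at screening and at later visits. Its reporting rule is: "Changes noted in subsequent exams when compared to the baseline exam will be reported as an adverse event". It gives no direction of change, no significance threshold, no exception for lymphoma findings and no cross-reference to Section 7.

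Section 7.2 sets the definition: "An adverse event is defined as any untoward medical occurrence in a clinical trial subject". For a pre-existing condition it requires deterioration: "Worsening indicates that the pre-existing medical condition has increased in severity, frequency, and/or duration", or an association with a worse outcome. On the lymphoma itself it says two things. Disease progression "as assessed by measurement of malignant lesions on radiographs or other methods should not be reported as adverse events". But also: "Worsening of signs and symptoms of the malignancy under study should also be reported as adverse events in the appropriate section of the CRF".

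Section 7.4.1 has a significance filter, for laboratory results only: "In general, abnormal laboratory findings without clinical significance (based on the Investigator's judgment) are not to be recorded as adverse events".

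The primary endpoint in 12.1 is "Rate and severity of RT-related toxicity as per CTCAE v5.0 criteria during RT or within the first 30 days of completing RT". The safety analysis in 12.4 tabulates "Subject incidence rates of adverse events including all, serious, fatal, CTCAE version 5.0 Grade 3 or higher and treatment related AEs". Section 12.5 adds a comparison of safety endpoints with historical controls who did not have RT.

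**The concern.** The patients are irradiated at a refractory lymphoma site. If that site is palpable and responds, the exam changes. Under 9.4 as written the response must be recorded as an adverse event, and so must any harmless change elsewhere on exam. Section 7.4.1 then asks for a yes or no on whether the event is related to RT. For shrinkage of an irradiated mass the natural answer is yes, so the record could reach the treatment-related rows as well as the all-AE rows of 12.4.

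The all-AE incidence would then mix toxicity with response and with findings of no consequence, and it would depend on whether the person recording follows 9.4 or 7.2. Exams are scheduled weekly during RT, so there are repeated occasions for this. Nothing in the documents says the historical controls in 12.5 were recorded under a rule like 9.4, so a recording difference could pass for a difference in toxicity. Section 12.2 also plans to size a larger study from the safety events seen here.

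**Working it through.** The plan states no adverse event rate, so there is no figure of its own to reproduce. The check is a comparison of the two rules, finding by finding, and then the weight of one patient.

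**Step 1. The same exam finding under each section**

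| Exam finding | 9.4 read literally | 7.2 | Agree? |
|---|---|---|---|
| Palpable irradiated mass is smaller | AE | Not an AE: neither untoward nor worsened | No |
| Neutral change without clinical significance | AE | Not an AE: not untoward | No |
| Lymphoma lesion larger, recorded only as a measurement | AE | Not an AE: measured progression is excluded | No |
| Lymphoma growth showing as a worse sign or symptom | AE | AE: explicitly reportable | Yes |
| New or worsened untoward finding, for example dermatitis | AE | AE | Yes |

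The contradiction is confined to the first three rows. The 7.4.1 significance filter does not settle them, because it covers laboratory findings and not exam findings.

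**Step 2. Which outputs are exposed**

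- *Primary endpoint (12.1).* It needs toxicity, a CTCAE v5.0 grade and RT attribution. Attribution removes most neutral changes. It does not remove shrinkage of the irradiated mass, but an improvement is not a toxicity and has no severity to grade. Largely protected.
- *Stopping rule (12.3).* It needs grade 4 or higher, attributed to RT and not to lymphoma progression. Largely protected.
- *Serious, fatal and Grade 3 or higher rows (12.4).* Benign exam changes would not reach them.
- *All-AE row (12.4).* Fully exposed.
- *Treatment-related row (12.4).* Exposed where the change is judged related to RT.
- *Historical comparison (12.5).* Exposed to the extent that it uses those rows.

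Exposure is also limited in time. Under 7.4.1, only targeted categories of event are collected after 3 months post-RT.

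**Step 3. Size**

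Input from the documents: planned enrolment of 20 (12.2). One patient counted only for a benign exam change adds 1/20 = 0.05, or 5 percentage points.

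The total needs two quantities the documents do not give, so both are assumed here: *q*, the true any-AE risk, and *s*, the share of the remaining patients whose only record is a benign exam change. Then

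recorded any-AE incidence = q + (1 − q)s, and the rise is (1 − q)s.

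| q (assumed) | s = 0.1 | s = 0.3 | s = 0.5 |
|---|---|---|---|
| 0.5 | 0.55 | 0.65 | 0.75 |
| 0.7 | 0.73 | 0.79 | 0.85 |
| 0.9 | 0.91 | 0.93 | 0.95 |

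The smallest rise is (1 − 0.9) × 0.1 = 0.01, or 1 point. The largest is (1 − 0.5) × 0.5 = 0.25, or 25 points. This range shows only how strongly the result depends on the assumptions. It is not an estimate for this trial.

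**The case against.** The best defence is that Section 7 is the governing text on adverse events, while Section 9 describes its contents as an overview of assessments and procedures. Someone who starts from 7.2 would not record a shrinking tumour, and the reporting form, which asks for a diagnosis or symptom and a severity, does not suit one. That makes literal use of 9.4 less likely. It does not remove the contradiction: 9.4 is mandatory, it does not point to 7.2, and no sentence says which section prevails.

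The defence is right that several stronger readings fail.

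- A reader might infer that all lymphoma growth found on exam is an adverse event under 9.4 but not under 7.2. Section 7.2 excludes progression assessed by measurement, yet it requires worsening signs and symptoms of the malignancy to be reported. Growth that shows in that way is an adverse event under both sections.
- A reader might infer that rates would differ between sites. Section 2.1 describes a single-center study, so any inconsistency would be between the people recording.
- A reader might suppose that change in a palpable mass is the most frequent exam change and that a large part of the any-AE rate would be spurious. Eligibility requires a lesion measurable by Lugano criteria, not a palpable one, and no document gives the frequency of exam changes.

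**Conclusion.** The conflict is real and narrow. Section 9.4 contradicts 7.2 for improved findings, for neutral findings, and for progression recorded only as a lesion measurement. If 9.4 is followed literally, the descriptive all-AE table, possibly the treatment-related table, and the historical comparison can include findings that are not toxicity.

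The firm figure is 5 points per patient so counted, given 20 patients. The total cannot be derived from the documents. It would be zero if 7.2 is followed throughout. A reader might conclude that the adverse event rates are inflated, or that the primary safety result is compromised. The text supports neither: inflation depends on how staff apply 9.4, and the primary endpoint and stopping rule are largely shielded by grading and attribution. It is a modest point, but worth correcting in a trial whose primary objective is safety.

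**What to change.** Replace the reporting sentence in 9.4 with:

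> New or worsened, clinically significant findings compared with the baseline exam that meet the adverse event definition in Section 7.2 will be reported as adverse events and graded by CTCAE v5.0. Improvement is not an adverse event. Disease progression assessed only by lesion measurement is recorded as disease assessment (Section 10.1); worsening signs or symptoms of lymphoma remain reportable as adverse events under Section 7.2.

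The final clause is needed. A rule that sent every change in a lymphoma lesion to disease assessment would create a new conflict with 7.2.

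The cost is three sentences in place of one. No visit, assessment or analysis changes, and exam findings stay in the medical record. If patients have already been enrolled, adverse event entries that rest only on an exam change should be checked against the new wording before the 12.4 tables are produced.

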9.5 Laboratory

The below samples will be collected at the time points indicated in the SOA. Additional samples (eg, blood, tissue, etc) may be collected as needed for further safety testing.

Local lab analysis:

- Sodium (Na), potassium (K), chloride (Cl), total CO₂ (bicarbonate), creatinine, glucose, blood urea nitrogen (BUN) **or urea (if BUN test cannot be analyzed by the local lab)**, albumin, calcium total, magnesium total (Mg), inorganic phosphorus, alkaline phosphatase, ALT/GPT, AST/GOT, total bilirubin, direct bilirubin, LDH, uric acid
- C-reactive protein (CRP)
- Complete Blood Count (CBC) with Differential
- A urine or serum sample will be collected and assessed locally for females of childbearing potential. If the screening pregnancy test is positive, the subjects should not be enrolled.

- **Additional blood draws for PBMC and serum, as well as tissue may be collected and stored locally for subsequent translational research studies to include, but not limited to, cytokine analysis, FLOW and expression phenotyping, DNA/RNA sequencing, IHC/RNA ISH, and/or correlative studies.**
- Blood draws for PBMC (lymphocyte subsets, and anti-CD19 CAR T cell levels) and cytokine analysis will be performed at intervals outlined in the SOA.
- Archived tumor tissue
 - Fresh tumor samples will be collected for central pathology review and evaluation of prognostic markers specific for **large B-cell lymphoma** and pertaining to the tumor immune environment. Additional analysis may include CD19 expression, gene expression profiling, and analysis of **tumor-specific** DNA alterations. Remaining tumor samples may be stored for future exploratory analysis of DNA (somatic mutations), RNA, or protein markers.

